#### **Treatment grouping 1 (TG1) for Placebo controlled period from Day 1 to Week 26:**

- *Placebo (Pbo)*
- *Linagliptin 5 mg (L5)*
- *Empagliflozin pooled (E Pooled)*, consisting of
  - Empagliflozin 10 mg responders at Week 12 to 10 mg (E10R-10)
  - Empagliflozin 10 mg non-responders at Week 12 to 10 mg (E10NR-10)
  - Empagliflozin 10 mg non-responders at Week 12 to 25 mg (E10NR-25)
  - Empagliflozin 10 mg and not proceed to re-randomisation at Week 14 (E10)

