## 7.8 SAFETY ANALYSIS

### Primary safety analysis (Comparison vs. placebo) (up to Week 26)

The primary safety analysis will be based on the TS. All safety variables will be analysed from start of initial randomised treatment until Week 26 (except for AEs, which will be analysed up to the day before Week 26). The treatment grouping 1 will be used for the comparisons and presented for DINAMO and DINAMO Mono separately.

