#### 7.8.1.1 Assignment of AEs to treatment

In general, the analysis of adverse events will be based on the concept of treatment emergent adverse events. This means that all adverse events occurring between first randomised or re-randomised drug intake until 7 days after last drug intake or cut-off (depending on analysis period, see [Section 7.8](#)) will be assigned to the randomised treatment.

In general, in-text AE tables will only present AEs assigned to the randomised treatment taken. For listings, AE will be assigned to one of the treatment phases of pre-treatment, treatment groups (depending on treatment grouping), post-treatment, post-study.

The cut off for the AEs outputs presentation period will be defined as the following.

- Prior to Week 26 treatment: Cut off at Visit 5 treatment date. If Visit 5 treatment date is not available, then the minimum of Day 183 or end of study date.
- Up to Week 52 present the whole treatment period plus the residual effect period.

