#### 7.8.1.3 AE summaries

An overall summary of adverse events will be presented by TG1, TG6, TG5 and TG4.

The frequency of patients with adverse events will be summarised by treatment, primary system organ class and preferred term. AEs will also be reported by intensity. Separate tables will be provided for patients with other significant adverse events according to ICH E3 (6), for patients with serious adverse events, for patients with AEs leading to discontinuation, for patients with drug-related AEs and for patients with selected AESIs and other specific AEs. Incidence rate as defined in [Section 7.8.1.8](#) will apply to frequency tables: overall summary of AEs, patients with AEs, patients with drug-related AEs, patients with other significant AEs according to ICH E3, patients with AEs leading to discontinuation and patients with SAEs. All above mentioned tables will be repeated by TG1, TG6, TG5 and TG4.

The system organ classes will be sorted in descending order of the total frequency count of all treatments then followed by preferred terms in descending order of the total frequency count. Alphabetical ordering will be used for the same total frequency counts on PT level.

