#### 7.8.1.8 AE incidence rates

In addition to the frequency tabulations, time-adjusted adverse event analyses will be performed for on-treatment AEs and on-treatment AEs by SOC, respectively HLT and PT.

The time at risk in patient years for an AE is derived as follows:

Patients with AE:

time at risk (AE) in days = date of start of AE with specified PT/SOC/HLT – initial randomised treatment start date + 1

Patients without AE:

time at risk (AE) in days = end date of time at risk – initial randomised treatment start date + 1,

where end date of time at risk is the minimum of date of last study drug intake + x days and date of death, if applicable.

The standard approach will be x=7 days, but for certain AEs in addition other approaches will be used.

Total AE-specific time at risk per treatment group is then derived as:

Time at risk (AE) [years] = Sum of time at risk [days] over all patients in a treatment group/365.25

For 'each row of a table' (e.g. displaying an SOC), time at risk is calculated using start of first AE summarised in this row; e.g. for patient with AE in a specified SOC, time at risk = date of start of AE with specified PT in this SOC – start of initial randomised treatment + 1.

The AE incidence rate per 100 patient years at risk will then be calculated as follows:

Incidence rate per 100 patient years (pt-yrs) = 100\*number of patients with AE / time at risk (AE) [years].

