#### 7.8.1.9 COVID-19

In order to assess the impact of COVID-19 on the reporting of any adverse events, frequency of patients and rate of AEs before and from the start of COVID-19 disruption up to the day before Week 26 by TG1 and up to Week 52 by TG6 will be presented for DINAMO only. In general, the time at risk is the entire treatment duration plus residual effect period. The time at risk for the period before start of COVID-19 disruption is defined as first dose of treatment until either the day before COVID-19 start date or Treatment end date plus residual effect

period (whichever comes earlier). The time at risk for the period from start of COVID-19 disruption is defined as COVID-19 start date or treatment start date (whichever comes later) until treatment end date plus residual effect period. The residual effect period is within 7 days of treatment end date for treatment groups without a re-randomised treatment to follow on. Treatment emergent AEs occurred in the residual effect period after end of treatment will be counted toward the specific defined period based on the COVID-19 start date. For TG1, the residual effect period will not be added for patients who are still on treatment at Week 26 and the cut off for the AEs prior to Week 26 treatment will also apply.

Patients with a SARS-CoV-2 infection will be identified based on the narrow BICMQ 'SARS-CoV-2 infections' plus the PT 'Suspected COVID-19'. A listing of these AEs will be provided. The patients with such on-treatment AEs will define the subgroup of SARS-CoV-2 infected patients and for this subgroup the following AE analyses will be provided for TG1 and TG6:

- Overall summary of AEs
- Number of patients with AEs by SOC and PT
- Number of patients with AEs leading to discontinuation by SOC and PT
- Number of patients with SAEs by SOC and PT

To provide all available AE information on COVID-19 testing or infection status an additional listing will present all AEs related to SARS-CoV-2 infection based on the broad MedDRA SMQ 'COVID-19'.

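### The AE incidence-rate rule in SAP 7.8.1.8 does not carry over the Week 26 cut-off, so for TG1 the written person-time does not match the events counted

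*SAP*

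**What the plan says.** SAP 7.8.1.8 defines time at risk once, for every treatment grouping. A patient with the AE contributes the time to its onset. A patient without it contributes the days from the first dose of initially randomised treatment, counting both ends, to an end date that the SAP fixes as follows: "end date of time at risk is the minimum of date of last study drug intake + x days and date of death". On the value of x, the section adds: "The standard approach will be x=7 days"; other values may be used in addition for certain AEs. The section does not mention an analysis period or re-randomisation.

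SAP 7.8.1.3 attaches these rates to the overall AE summary and to the tables of all AEs, drug-related AEs, other significant AEs, AEs leading to discontinuation, and SAEs: "All above mentioned tables will be repeated by TG1, TG6, TG5 and TG4". Table 6.3: 1 also lists the AE incidence rate for TG1 and TG5.

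TG1 is defined in SAP 6.1 as the "Placebo controlled period from Day 1 to Week 26". SAP 7.8 makes it the primary safety comparison, with safety variables taken to Week 26, "except for AEs, which will be analysed up to the day before Week 26". SAP 7.8.1.1 gives the event cut-off: "Prior to Week 26 treatment: Cut off at Visit 5 treatment date". If there is no Visit 5 treatment date, the fallback is the earlier of Day 183 and the end of study.

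Three other places bound TG1 in time:
- SAP Table 7.7: 1 sets the TG1 last administration at one day before the Week 26 intake, for the exposure displays.
- SAP 7.8.1.9 limits time at risk for the COVID-19 AE rates: "For TG1, the residual effect period will not be added for patients who are still on treatment at Week 26". It adds that the Week 26 AE cut-off applies there too.
- Protocol 7.3 censors, for analyses up to Week 26, data collected after the first study drug intake of the extension.

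**The concern.** A rate is interpretable only if events and person-time come from the same window. In TG1 the events stop at Visit 5. The written denominator runs on to the last study drug intake, which for a completer falls at about Week 52, plus 7 days. No TG1 event can be counted in that added time.

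For the placebo arm the mismatch also concerns treatment. Placebo patients are re-randomised at Week 26 to linagliptin or empagliflozin (protocol 3.1), so their last study drug intake is an active dose. Followed literally, the placebo rate would have about 26 weeks of active-drug exposure in its denominator.

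At stake are the absolute TG1 rates per 100 patient-years and, for common AEs, the ratios between arms. The start of the clock is right for TG1; the point concerns only its end.

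**Working it through.** The documents state no incidence rate or person-time total, so there is no planned figure to reproduce. The check applies the SAP formula to a patient who completes 52 weeks without the AE.

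**Inputs**
- Start: Day 1 (SAP 7.8.1.8).
- Week 26 visit: planned Day 183. Week 52 / EoT: planned Day 365 (SAP Table 6.7: 2).
- x = 7 days (SAP 7.8.1.8).
- TG1 AE window: to the day before Week 26 (SAP 7.8), i.e. Day 182. Counting the Visit 5 date itself gives 183.

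**Days at risk = end date − start date + 1**
- Matched to the TG1 window: 182 − 1 + 1 = **182**.
- SAP 7.8.1.8 read literally: (365 + 7) − 1 + 1 = **372**. The ratio is 372/182 = 2.04. The excess is 372 − 182 = 190 days, or 190/372 = 51% of the total. For a placebo completer, Days 183 to 365 (183 days) are on active drug and 7 are residual.
- Last intake taken as the TG1 date in Table 7.7: 1, plus 7: 182 + 7 = **189**. The ratio is 189/182 = 1.038, and all 7 extra days fall after the switch.
- Protocol 7.3 censoring also applied to person-time: the clock stops at the first extension intake, giving 182 or 183 days and an error of about zero.

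**Effect on rates.** The documents give no AE frequencies, so the proportion p of patients with the AE by Week 26 is an assumption, shown over a range. Also assumed are a constant hazard to Day 182, full completion of 52 weeks, and a patient whose first AE comes after the cut-off counted as without AE. With E the days contributed by a patient without the AE:
- λ = −ln(1 − p)/182
- mean days to the AE among those who have it: m = 1/λ − 182(1 − p)/p
- rate per 100 patient-years = 100 · p · 365.25 / [p·m + (1 − p)·E]

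Example, p = 10%: λ = 0.10536/182, so 1/λ = 1727.4 and m = 1727.4 − 1638 = 89.4. The mean days at risk are 8.94 + 0.9 × 182 = 172.74 (matched) and 8.94 + 0.9 × 372 = 343.74 (literal). The rates are 3652.5/172.74 = 21.1 and 3652.5/343.74 = 10.6.

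| p | Matched (182) | Literal (372) | Literal / matched | Table 7.7: 1 date + 7 (189) | 189 / matched |
|---|---|---|---|---|---|
| 2% | 4.1 | 2.0 | 0.492 | 3.9 | 0.963 |
| 5% | 10.3 | 5.1 | 0.496 | 9.9 | 0.964 |
| 10% | 21.1 | 10.6 | 0.503 | 20.4 | 0.965 |
| 30% | 71.6 | 38.3 | 0.535 | 69.4 | 0.969 |
| 50% | 139.1 | 80.7 | 0.580 | 135.5 | 0.974 |
| 70% | 241.6 | 157.0 | 0.650 | 236.9 | 0.981 |

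**Effect on between-arm rate ratios**

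| Risks compared | Matched | Literal | Table 7.7: 1 date + 7 |
|---|---|---|---|
| 10% v 5% | 2.05 | 2.08 | 2.06 |
| 70% v 50% | 1.74 | 1.95 | 1.75 |

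**The case against.** The best defence is that SAP 7.8.1.8 should not be read alone. The SAP builds on section 7 of the protocol, and protocol 7.3 censors post-switch data for analyses up to Week 26. TG1 is defined as ending at Week 26. SAP 7.8.1.1 sets the cut-off for the same AE outputs to which SAP 7.8.1.3 adds the rates. SAP Table 7.7: 1 is the only place that gives a period-specific last administration. SAP 7.8.1.9 refers to the AE cut-off as an existing rule. To reach 372 days, a programmer would have to set all of this aside. SAP 7.8.1 also cites a company standard for AE reporting that is not among the documents and may define time at risk by period.

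Much of this stands. It makes it likely that a cap was intended, and a reader should not infer that the TG1 rates will in fact be halved. The documents support only that the written formula gives that result if followed literally. Nor does post-Week-26 time enter under every reading: with protocol 7.3 applied to person-time it does not.

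The defence does not remove the gap. Protocol 7.3 concerns collected data and does not amend the explicit formula of last intake plus 7 days. The cap on time at risk is written only for the COVID-19 tables, and the Table 7.7: 1 date only for exposure. Borrowing that date and then adding 7 days still leaves a post-switch week in the denominator.

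The limits on consequence also stand. Protocol 7.3.6 makes the safety analyses descriptive, without hypothesis tests. The rates supplement the frequency tables, which are unaffected. Patients who stop before Week 26 add no post-switch active-drug time.

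**Conclusion.** The written rule needs correcting. SAP 7.8.1.8 has no Week 26 limit for TG1, and the passages that suggest one do not change its formula.

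The size depends on how the gap is filled. The literal reading gives absolute TG1 rates of about 0.50 to 0.65 of the correct value, the Table 7.7: 1 date plus 7 days gives rates about 2–4% too low, and protocol 7.3 censoring of person-time gives about zero error. The first two figures assume full completion, a constant hazard and the AE proportions shown; earlier discontinuation would make the literal error smaller.

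A reader might infer a general bias in the comparison with placebo. The figures do not support that for rare AEs, because all three arms carry the extra time and the ratios barely move. Distortion of the ratios appears for common AEs. Specific to placebo is that the added time is spent on a different treatment. Efficacy, type I error, and AE counts and percentages are untouched.

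**What to change.** Add to SAP 7.8.1.8 that, for TG1, the end of time at risk is the earliest of:
- the SAP 7.8.1.1 cut-off (Visit 5 treatment date, or its stated fallback),
- last study drug intake plus 7 days,
- death.

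State that no residual period is added for patients still on treatment at Week 26, as SAP 7.8.1.9 already provides for the COVID-19 tables. State also that a patient whose first AE falls after the cut-off counts as without the AE and is censored at the cut-off.

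The cost is a short addition to the SAP text and one date in the derivation. No new data are needed.

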#### 7.8.1.9 COVID-19

In order to assess the impact of COVID-19 on the reporting of any adverse events, frequency of patients and rate of AEs before and from the start of COVID-19 disruption up to the day before Week 26 by TG1 and up to Week 52 by TG6 will be presented for DINAMO only. In general, the time at risk is the entire treatment duration plus residual effect period. The time at risk for the period before start of COVID-19 disruption is defined as first dose of treatment until either the day before COVID-19 start date or Treatment end date plus residual effect

period (whichever comes earlier). The time at risk for the period from start of COVID-19 disruption is defined as COVID-19 start date or treatment start date (whichever comes later) until treatment end date plus residual effect period. The residual effect period is within 7 days of treatment end date for treatment groups without a re-randomised treatment to follow on. Treatment emergent AEs occurred in the residual effect period after end of treatment will be counted toward the specific defined period based on the COVID-19 start date. For TG1, the residual effect period will not be added for patients who are still on treatment at Week 26 and the cut off for the AEs prior to Week 26 treatment will also apply.

Patients with a SARS-CoV-2 infection will be identified based on the narrow BICMQ 'SARS-CoV-2 infections' plus the PT 'Suspected COVID-19'. A listing of these AEs will be provided. The patients with such on-treatment AEs will define the subgroup of SARS-CoV-2 infected patients and for this subgroup the following AE analyses will be provided for TG1 and TG6:

- Overall summary of AEs
- Number of patients with AEs by SOC and PT
- Number of patients with AEs leading to discontinuation by SOC and PT
- Number of patients with SAEs by SOC and PT

To provide all available AE information on COVID-19 testing or infection status an additional listing will present all AEs related to SARS-CoV-2 infection based on the broad MedDRA SMQ 'COVID-19'.

### 7.8.2 Laboratory data

The analyses of laboratory data will be descriptive in nature for DINAMO and DINAMO Mono separately. The results will be performed for the primary safety analysis (TG1) and long term safety (TG5), presented based on SI units. The naming of the lab parameters will follow CTP. Some selected analyses will be repeated in conventional units and presented in Appendix 16.1.13.1.

The process of normalisation as well as standard analyses for safety laboratory data are described in the BI guidance for the Display and Analysis of Laboratory Data (7). All analyses considering multiple of times upper limit of normal (ULN) will be based on original and not normalised data.

Only patients with at least one available on-treatment value regardless of intake of rescue medication (OC-ROC) will be included in the analysis of an individual laboratory parameter. All individual data will be presented in listings.

#### 7.8.2.1 General laboratory evaluation

The following general laboratory evaluations will be performed for all laboratory data captured in the study including bone metabolism biomarkers (Calcium, phosphate, alkaline phosphatase, 25-OH-vitamin D, intact parathyroid hormone, serum N-terminal cross-linked telopeptide (NTx)). But excluding HBA1C, FPG, C-peptide and UACR that are separately

described in the planned efficacy analysis, and other biomarkers that are separately described in [Section 7.8.2.3](#), [7.8.2.4](#) and [7.8.2.5](#)):

- For quantitative lab results, descriptive statistics per treatment group at baseline, last value on-treatment, and change from baseline to last value on-treatment (in both SI and conventional units)
  - If both the BI adult standard and the central lab standard ranges are available, the descriptive statistics will be performed on the normalised value.
    - Exception to NTx: the central lab standard range of female with tanner stage 5 will be used as the BI standard reference range.
  - Otherwise, the descriptive statistics will be performed on the standardised value
- For qualitative lab results, frequency tables per treatment group will be presented at baseline and at last value on treatment (only in SI unit).
  - Erythrocytes and leukocytes in urine analysis will be analysed as categorical data with 2 categories (“Normal” and “High”).
- Frequency table per treatment group will summarise the number of patients within and outside the reference range at baseline and the last measurement on treatment (only in SI unit).
  - The age dependent reference range used for post-baseline values by the lab will be replaced by the reference range as provided for the respective patients' baseline measurement, and re-categorised.
  - Exclude parameters only measured occasionally.
- Frequency tables (include a patient listing) per treatment group will summarise the number of patients with any potentially clinically significant abnormality (PCSA) using company standard clinically significant criteria. PCSA will be determined based on SI units and only be counted in tables if the patient had no PCSA value at baseline.

All the above analyses will be performed on the appropriate treated set for TG1 and TG5. The PCSA tables will additionally be produced for TG6 and TG4 (from Week 14 up to Week 52).

- For quantitative lab results (as described above), descriptive statistics tables will be displayed per treatment group and per analysis visit over time for TG1 and TG5 in Appendix 16.1.13.

#### 7.8.2.2 Elevated liver enzymes

Special attention will be paid to parameters characterising liver function. These include liver enzymes (alanine aminotransferase (ALT), aspartate aminotransferase (AST), alkaline phosphatase (AP)) and total bilirubin (TBILI).

The frequency of the number of patients with AST/ALT elevations  $\geq 3xULN$ ,  $\geq 5xULN$ ,  $\geq 10xULN$ , and  $\geq 20xULN$  will be displayed.

To support analyses of liver related adverse drug effects, patients with AST and/or ALT  $\geq$  3xULN with concomitant or subsequent TBILI  $\geq$  2xULN in a 30 day period after AST/ALT elevation are of special interest.

Patients with elevations as defined above by ALT and/or AST, total bilirubin and AP combinations, will be summarised and further classified by AP  $<$  2xULN and  $\geq$  2xULN, where AP is the maximum value in the 30 day period.

This analysis will be performed for the primary safety analysis (TG1), long term safety (TG5) and the safety during active treatment (TG6). For the definition of safety analyses see [Section 7.8](#).

Details on patients with elevated liver enzymes will be listed using the TS.

#### 7.8.2.3 Lipid parameters

Descriptive statistics over time up to 26 weeks by treatment grouping 1 and up to 52 weeks by treatment grouping 5 for the treated set (OC-ROC).

For each lipid parameter, see CTP in-text Table 5.3.3:1, separate MMRM models for change from baseline up to Week 26 will be fitted on the treated set (OC-ROC) by TG1. The models will include treatment, visit and visit-by-treatment interaction as fixed categorical effects, as well as the categorical covariate age at randomisation and the continuous covariates baseline lipid parameter, baseline HbA1c, baseline lipid parameter by visit, baseline HbA1c by visit. An unstructured (co)variance structure will be used to model the within patient measurements, and the same other options as used for the primary family of MMRM analysis model, as described in [Section 7.4.1.3\(A\)](#), will apply.

All analyses in this section will be repeated for parameters in conventional unit and presented in Appendix 16.1.13.

#### 7.8.2.4 Renal laboratory parameters

##### Creatinine and eGFR

All calculations for the grading of renal function will be based on the originally measured laboratory values, not on normalised values with BI standard reference ranges.

The glomerular filtration rate will be estimated according to Zappitelli (8):

$$\text{eGFR [mL/min/1.73m}^2\text{]} = \frac{(507.76 \times e^{0.003(\text{height})})}{(\text{Cystatin C}^{0.635} \times \text{Serum Creatinine}^{0.547})}$$

If renal transplant, x 1.165

(With height in cm, Cystatin C in mg/L and Serum Creatinine in  $\mu\text{mol/L}$ )

For the analysis of eGFR and for the covariates in the efficacy statistical modelling the values calculated from the above formula using the serum creatinine values from the central laboratory will be used, and not the eGFR values provided by the central laboratory. The endpoint will be derived at the visits where both serum creatinine and serum cystatin C are measured at the central laboratory.

A shift table from baseline to last value on treatment, (and from baseline to minimum value on treatment) will be provided for the time period up to 26 weeks.

Descriptive statistics will also be created for creatinine and eGFR values over time up to 26 weeks by treatment grouping 1 and up to 52 weeks by treatment grouping 5.

Additionally, summary tables will be created representing the number of patients per treatment group (i.e. TG1 (up to 26 weeks) and TG5 (up to 52 weeks)) who experienced a doubling in creatinine on treatment as compared to baseline and who were out of the normal range.

The UACR will be derived with the following formula.

$$\text{UACR [mg/g crea]} = \frac{\text{Urine Albumin [g/L]} \times 100}{\text{Urine Creatinine [mmol/L]} \times 0.011312217195}$$

A shift table from baseline value to last and maximum values on-treatment will be provided based on the following UACR categories (which used the derived UACR and not the albumin/creatinine ratio values provided by the lab): normal (< 30 mg/g crea), microalbuminuria (30 to <= 300 mg/g crea), macroalbuminuria (> 300 mg/g crea) by TG1 and TG5.

